12.2. Serious Adverse Events

A SAE is any untoward medical occurrence or effect that fulfills the following criteria:

- Results in death
- Is life-threatening (NOTE: the term "life-threatening" refers to an event in which the patient was at risk of death at the time of the event; it does not refer to an event which hypothetically might have caused death if it were more severe)
- Requires hospitalization or prolongation of existing inpatient hospitalization

- Results in persistent or significant disability or incapacity
- Is a congenital abnormality/birth defect
- Important medical events not captured by the above but which may, for example, require medical intervention to prevent one of the outcomes above.

Medical and scientific judgment should be exercised in deciding whether expedited reporting is appropriate in other situations, such as important medical events that may not be immediately life-threatening or result in death or hospitalization but may jeopardize the patient or may require intervention to prevent one of the other outcomes listed in the definition above. These should also usually be considered serious. Examples of such events are intensive treatment in an emergency room or at home for allergic bronchospasm; blood dyscrasias or convulsions that do not result in hospitalization; or development of drug dependency or drug abuse.

12.3. Reporting of Serious Adverse Events

Investigator reporting requirements for SAEs will be managed on behalf of the Sponsor by PPD. Full details of the procedures to be adopted will be documented in a safety management plan approved by responsible parties, in brief:

Any SAE which occurs to any patient from the time written informed consent is signed through the last visit must be reported by the Investigator. All SAEs that occur within 90 days of the last dose of treatment with the investigational drug, whether or not considered related to the investigational product, must also be reported. Any SAE that is ongoing when the patient completes the study or discontinues from the study will be followed by the Investigator until the event has resolved, stabilized, or returned to baseline status or the patient is lost to follow-up.

Any AE considered serious by the Investigator or Sub-Investigator or that meets serious criteria should be reported to PPD Pharmacovigilance (PVG) using the remote data capture (RDC) system. Data entry must be completed within 24 hours from the time the study site personnel first learned of the event.

In the event that RDC entry is not possible (e.g., system failure or access problems), the study site should complete the paper SAE report form and fax the form to PPD PVG within 24 hours of awareness of the event. The RDC system should be updated as soon as it is available.

Contact information for the PPD Pharmacovigilance Center:

SAE [contact]

SAE Fax line: [name]

The initial report should be promptly followed by detailed, written reports, which will include copies of hospital case records, discharge summaries, autopsy reports and other documents when requested and applicable. For unrelated cases, a full detailed case description may negate the need for additional hospital case records, discharge summaries, etc.

12.4. Monitoring of Patients with Adverse Events

Investigators must carefully monitor each patient for AEs. This includes clinical laboratory variables. Assessments must be made of the seriousness, severity, and relationship to the

administration of the investigational drug. After the initial AE/SAE report the Investigator is required to follow up proactively each patient and provide further information to PPD on the patient's condition. During the study, all AE/SAEs should be followed up until resolved, stabilized, or returned to baseline status or patient is lost to follow-up, unless the event is considered by the Investigator to be unlikely to resolve due to the patient's underlying disease.

12.5. Procedures to be followed in the Event of Abnormal Laboratory Test Values

In the event of unexplained abnormal laboratory test values, the tests should be repeated immediately and followed up until they have returned to the normal range and/or an adequate explanation of the abnormality is found. For abnormal laboratory test values related to AEs of special interest, refer to Section 11.5.

12.6. Clinical Laboratory Parameters and Abnormal Laboratory Test Results

Clinically significant changes, in the judgment of the Investigator, in laboratory parameters (abnormalities) will be recorded as AEs.

During the treatment period, all Total WBC and WBC differential results will be blinded. Reductions in ALC levels is a known pharmacodynamic effect of RPC1063. If any of the following results are observed, the Investigator will be notified and asked to repeat the laboratory tests within approximately 7 days:

- Absolute lymphocyte count [ALC] < 200 cells/ μ L
- Absolute neutrophil count [ANC] < 1000 cells/ μ L
- Total WBC > 20,000 cells/ μ L

If the repeat values also exceed these limits, the Investigator will be informed that the patient's results for the abnormal parameter have fallen below the acceptable threshold.

If ANC or total WBC counts are confirmed below the acceptable limits, the Medical Monitor will contact the treating investigator to request close monitoring for risk of serious infection and appropriate follow-up, at the discretion of the investigator.

If the ALC is confirmed < 200 cells/ μ L, the Investigator will temporarily discontinue investigational drug and then consult with the Medical Monitor. Laboratory testing will be repeated weekly until ALC is > 500 cells/ μ L.

When ALC has returned to > 500 cells/ μ L, the treatment may be reinitiated at the Investigator's discretion (Section 9.6.2 for instructions on resuming treatment after missing doses). For patients whose ALC level is confirmed < 200 cells/ μ L and has not reached the acceptable range (ALC > 500 cells/ μ L) during the study, laboratory testing will be repeated at the 90-day Safety Follow-up Visit.

If patients have elevations in ALT and/or AST \geq 3x the upper limit of normal (ULN), a retest should be performed as soon as possible but not later than 14 days after the original test. If the abnormality is confirmed, weekly testing should continue until ALT and AST are < 3x ULN. If the ALT and/or AST stabilizes at a level > 3x ULN, the Medical Monitor may agree to less

frequent testing. The Investigator should establish causality. In addition, the confirmed elevation $> 3x$ ULN is an adverse event of special interest (see Section 11.5) and should be reported by the Investigator.

At any time, if any of the following occur and there are no apparent alternative causes for the finding, the investigational drug must be permanently discontinued:

- ALT or AST $> 8x$ ULN or
- ALT or AST $> 5x$ ULN with confirmation, within 2 weeks or
- ALT or AST $> 3x$ ULN and (total bilirubin $> 2x$ ULN or INR > 1.5) or
- ALT or AST $> 3x$ ULN with the appearance of fatigue, nausea, vomiting, right upper quadrant pain or tenderness, fever, rash, and/or eosinophilia ($>5\%$).

The Investigator should establish causality.

After discontinuation due to elevation of ALT or AST $> 5x$ ULN or concurrent elevations of ALT or AST $> 3x$ ULN and bilirubin $> 2x$ ULN, further liver function evaluation should be performed (for example, coagulation panel and alkaline phosphatase) in consultation with the Medical Monitor.

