26. Treatment with any of the following drugs or interventions within the corresponding timeframe:
 - At randomization
 - CYP2C8 inhibitors (eg, gemfibrozil or clopidogrel) or inducers (eg, rifampicin)
 - Two weeks prior to randomization
 - Monoamine oxidase inhibitors (eg, selegiline, phenelzine)

Exclusions Related to Laboratory Results:

27. Serum creatinine > 1.4 mg/dL for women or > 1.6 mg/dL for men
28. Liver function impairment or persisting elevations of aspartate aminotransferase (AST) or alanine aminotransferase (ALT) > 2 times the upper limit of normal (ULN), or direct bilirubin > 1.5 times the ULN
29. Platelet count < 100,000/ μ L
30. Hgb < 8.5 g/dL
31. Neutrophils < 1500 / μ L
32. Absolute WBC count < 3500/ μ L
33. Absolute lymphocyte count < 800/ μ L
34. ECG showing any clinically significant abnormality (e.g., acute ischemia, any significant heart conduction abnormality [e.g., left bundle branch block])
35. FEV₁ or FVC < 70% of predicted values at screening

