11.3. Laboratory Safety Assessments

Analysis of samples will be conducted centrally by PPD Global Lab. Wherever possible during the Induction and Maintenance Period, Investigators should not send laboratory samples to their local labs as this may lead to unblinding of the treatment assignment given RPC1063's MoA (retention of systemic lymphocytes). Further details of the procedures to be followed for sample collection, storage, and shipment will be documented in a laboratory manual.

Additional and repeat laboratory safety testing may be performed at the discretion of the Investigator.

The following laboratory tests will be performed to assess the safety profile of RPC1063, as outlined in [Table 1](#) and [Table 2](#):

- Routine safety laboratory tests:
 - Hematology – red blood cell (RBC) count, total and differential WBC count (basophils, eosinophils, lymphocytes, monocytes, and neutrophils), platelet count, Hgb, hematocrit, mean corpuscular volume (MCV), mean corpuscular hemoglobin (MCH), and mean corpuscular hemoglobin concentration (MCHC). Total and differential WBC counts will not be provided to the Investigator to maintain the treatment blind during the Induction and Maintenance Period. These parameters and alerts for these parameters will be monitored by the PPD Safety Surveillance team.
 - Blood chemistry - sodium, potassium, chloride, calcium, magnesium, phosphate, blood urea nitrogen, random glucose, albumin, alkaline phosphatase, creatinine, ALT, AST, gamma glutamyltransferase (GGT), amylase, total bilirubin, conjugated bilirubin and CRP. CRP results will not be reported until completion of the study to maintain the treatment blind during the Induction and Maintenance Period. Abnormal laboratory parameters inconsistent with clinical presentation of UC or suspicious of underlying medical condition should be repeated for accuracy. If an increase of amylase above the clinically notable value (≥ 300 U/L) is observed at any post randomization visit, lipase should be tested to determine the origin of elevated amylase (pancreatic versus extra pancreatic).
 - Urinalysis - leukocytes, specific gravity, bilirubin, blood, glucose, ketones, pH, protein, and urobilinogen

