- Routine blood samples will be analyzed by the central laboratory. Blood samples taken at the screening visit are to be in the fasting state. Blood samples taken at subsequent visits are recommended to be in the fasting state. Details regarding collection of samples, shipment of samples, reporting of results, laboratory reference ranges, and alerting abnormal values will be supplied to the site before site initiation in a study laboratory manual. The results of the analysis will be made available to

each site by the central laboratory, at the earliest, 48 hours after receipt of the samples by the central laboratory.

- Investigators will be asked to comment on those abnormalities on the respective laboratory result page, including a notation of the clinical significance of each abnormal finding in the patient's source documents. The laboratory sheets will be filed with the patient's source documents. Abnormal laboratory values should not be recorded on the AE eCRF; however, any diagnoses (or signs or symptoms if a diagnosis is not possible) associated with the abnormal findings should be recorded on the AE eCRF.
- Pregnancy test: serum beta-hCG must be performed at screening in women of childbearing potential. Urine beta-hCG will be performed in women of childbearing potential at each scheduled visit. Between scheduled visits up until the 90-day Safety Follow-up Visit, monthly home urine pregnancy tests should be performed by the patient. If a urine pregnancy test result is positive, the Investigator will instruct the patient to suspend further RPC1063 dosing, if applicable, and schedule a follow-up appointment as soon as possible. A serum pregnancy test will be performed for confirmation, including after the 90-day Safety Follow-up Visit, if needed.
- Coagulation panel: prothrombin time (PT) and partial thromboplastin time (PTT). To be performed as scheduled in [Table 1](#) and [Table 2](#).
- Serology testing will be performed at screening to determine the patient's immune status with respect to several viruses; testing will be as follows:
 - anti-VZV IgG
 - HIV antibodies
 - HBsAg and HBcAg IgM
 - anti-HCV IgG or IgM

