6.20.6. Laboratory Assessments

Laboratory tests include the following:

- Hematology red blood cell (RBC) count, total and differential WBC count (basophils, eosinophils, lymphocytes, monocytes, and neutrophils), platelet count, hemoglobin (Hgb), hematocrit, mean corpuscular volume (MCV), mean corpuscular hemoglobin (MCH), and mean corpuscular hemoglobin concentration (MCHC). Total and differential WBC counts will not be provided to the Investigator to maintain the treatment blind. These parameters and alerts for these parameters will be monitored by the PPD Safety Surveillance team.
- Blood chemistry sodium, potassium, chloride, calcium, magnesium, phosphate, blood urea nitrogen, random glucose, albumin, alkaline phosphatase, creatinine, alanine aminotransferase, aspartate transaminase, gamma glutamyltransferase, amylase, total bilirubin, conjugated bilirubin.
- Urinalysis leukocytes, specific gravity, bilirubin, blood, glucose, ketones, pH, protein, and urobilinogen
- Pregnancy test: serum beta-hCG must be performed at screening in women of childbearing potential; urine beta-hCG will be performed at each visit, and if positive, do not dose, and confirm with a serum pregnancy test.
- Coagulation panel: prothrombin time and partial thromboplastin time.
- Serology testing will be performed at screening to determine the patient's immune status with respect to several viruses; testing will be as follows:

o anti-VZV IgG

- o HIV antibodies
- o anti-hepatitis A virus IgM
- o HBsAg and HBcAg IgM
- o anti-HCV IgG or IgM

Hematology, blood chemistry, and coagulation test results will be summarized at each study visit by treatment group for visits during the IP and MP and for all patients during the OLP. Changes from Visit 1 to the End of Study Visit will be summarized by treatment group.

Subjects with abnormalities in hematology assessments, defined as absolute lymphocyte count (ALC) <200 cells/uL, absolute neutrophil count (ANC) < 500 cells/uL as well as ANC <1000 cells/uL and total WBC >20,000 cells/uL will be summarized for each treatment group.

In addition, the change and percent change from baseline in CBC with Differential will be summarized for each treatment group.

The incidence of subjects with abnormalities in Liver Function Tests (SGPT/ALT, SGOT/AST, and GGT) will be summarized overall and at each visit for each treatment group for the following categories:

- > 1 x upper limit of normal (ULN)
- $\geq 2 \times ULN$

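### The total WBC alert is an upper limit, but the confirmed-result notice and the Medical Monitor step that follow it are worded for low counts

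*Protocol*

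**What the plan says.** Protocol 12.6 lists three results that prompt notification of the investigator and a repeat test within about a week: ALC < 200 cells/µL, ANC < 1000 cells/µL and "Total WBC > 20,000 cells"/µL. Two steps follow.

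- **Confirmed-result notice.** This covers all three parameters. It opens "If the repeat values also exceed these limits" and continues: "the Investigator will be informed that the patient's results for the abnormal parameter have fallen below the acceptable threshold".
- **Medical Monitor step.** This covers two parameters. It opens "If ANC or total WBC counts are confirmed below the acceptable limits". The Medical Monitor then asks the treating investigator to watch closely for serious infection, with follow-up left to the investigator's discretion.

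A confirmed low ALC has its own rule, a temporary drug hold, which is worded correctly.

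The SAP (6.20.6) agrees with the alert list on direction: "total WBC >20,000 cells/uL will be summarized for each treatment group". The only lower total WBC limit in either document is an entry criterion, exclusion 32 in Protocol 9.5.2: "Absolute WBC count < 3500"/µL.

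On blinding, Protocol 11.3 states: "Total and differential WBC counts will not be provided to the Investigator to maintain the treatment blind during the Induction and Maintenance Period".

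**The concern.** An upper-limit alert leads into two sentences written for lower limits. For total WBC the notice gives the wrong direction, and the condition for contacting the site about infection risk is one that the alert cannot satisfy.

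The direction matters because the site has little else to go on. During Induction and Maintenance it does not receive the total or differential count. Under Protocol 11.3, CRP is also held back until study completion, and investigators are asked to avoid local laboratories where possible. The notice is therefore the site's main information about what is abnormal. Serious or opportunistic infection is an adverse event of special interest in this trial (Protocol 9.1.2.1 and 11.5), and the faulty sentence is the one that asks for infection monitoring.

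The intended correction is also not certain. Either the follow-on wording should cover results outside a limit in both directions, or a low-WBC alert was meant and left off the list. Watching for infection could fit a high or a low count, so the action does not settle which.

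**Working it through.** The plan gives no figure to reproduce; the check is one of direction. Setting each alert limit in Protocol 12.6 against the two follow-on sentences:

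| Parameter | Alert limit (cells/µL) | Type | Notice wording fits? | Medical Monitor condition fits? |
|---|---|---|---|---|
| ALC | < 200 | lower | yes | not named (separate drug-hold rule) |
| ANC | < 1000 | lower | yes | yes |
| Total WBC | > 20,000 | upper | no | no |

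1. **Is the WBC direction itself a slip?** No sign of it. SAP 6.20.6 gives the same upper limit independently.
2. **Is there an on-treatment lower WBC limit for the wording to refer to?** None appears in either document. The < 3500/µL value applies at entry only.
3. **Is the trigger for the notice at fault?** No. Exceeding a limit can be read in either direction. The error lies in what the site is then told.
4. **What happens to a confirmed WBC above 20,000, read literally?** The first notification and the repeat test take place. The notice then calls the result low, and the Medical Monitor condition is not met. A count under 20,000 is not an alert at all.

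So the notice is wrong for 1 of 3 alerts, and the Medical Monitor condition for 1 of the 2 parameters that it names.

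**Possible frequency (illustrative).** Protocol Table 1 schedules post-dose haematology at Weeks 4, 8, 20 and 32, and about 180 patients are planned.

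- Lower bound, all patients leave after Week 8: 180 × 2 = 360 draws.
- Upper bound, all patients complete Maintenance: 180 × 4 = 720 draws.
- Assumed share of draws with a confirmed WBC above 20,000: 0.1% to 1%. The documents give no rate.
- Affected notices: 360 × 0.001 = 0.36 to 720 × 0.01 = 7.2.

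This takes every patient as reaching Week 8 and leaves out open-label draws.

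**The case against.** The strongest reply is that the intent can be inferred. The Medical Monitor sentence names total WBC, and the only on-treatment WBC limit is an upper one, so the reference has no function unless it means outside the limit. Investigators hold the protocol and could see that the notice conflicts with the alert list. Under Protocol 11.3 the contract research organization's safety surveillance team monitors the counts and alerts centrally. Protocol 12.5 asks for repeat and follow-up of unexplained abnormal values, and the DMC reviews safety about four times a year. The step itself is only a request for monitoring: no dose hold, discontinuation or unblinding depends on it. Protocol 11.3 also places the alert details elsewhere ("alerting abnormal values will be supplied to the site before site initiation in a study laboratory manual"), and that manual, which is not among the documents, may already be right. Finally, the event rate used above has no source.

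Most of this stands as a limit on harm. The rate is an assumption, and the finding does not rest on it. None of it corrects the rule. Inference cannot decide between a misworded step and a missing lower limit. Protocol 12.5 does not supply the Medical Monitor contact, and for a blinded count the site depends on what it is told. A conflict that an alert investigator might notice is still a conflict in a safety instruction.

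**Conclusion.** The concern holds. Protocol 12.6 is wrong as written for total WBC: followed literally, it misdescribes a confirmed high count and leaves out the infection-risk contact. Confidence in the textual contradiction is high. How often it would misdirect a site is unknown; 0.4 to 7 notices is a range under an assumed rate, not an estimate from the documents. Whether any site would actually be misled also depends on the laboratory manual.

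The ALC and ANC alerts are unaffected, as are the efficacy analyses. The point should be corrected because it sits in an operative safety rule and the remedy is small.

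**What to change.** In Protocol 12.6:

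- Reword the notice to say that the result is outside the acceptable limit, and state high or low for the parameter concerned.
- Reword the Medical Monitor condition as: ANC confirmed < 1000 cells/µL or total WBC confirmed > 20,000 cells/µL.
- If a low total WBC was also meant to prompt action, the clinical team should add a lower limit to the alert list.
- Check the alert text in the laboratory manual against the corrected wording.

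The cost is two sentences and a manual check. Existing limits, dosing rules, the SAP and all analyses stay as they are. Protocol 16.2 treats any protocol change as an amendment, so the correction could be included in the next one.

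### One limb of the permanent hepatic stop rule (ALT or AST >3x ULN with eosinophilia >5%) uses a blinded differential result, and no stated route brings that result to the site

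*Protocol*

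**What the plan says.** Protocol section 12.6 lists four liver-related conditions. If any occurs without another evident cause, "the investigational drug must be permanently discontinued". The fourth is ALT or AST above 3x ULN "with the appearance of fatigue, nausea, vomiting, right upper quadrant pain or tenderness, fever, rash, and/or eosinophilia", with eosinophilia defined as more than 5%.

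Protocol section 11.3 defines the hematology panel as including "total and differential WBC count (basophils, eosinophils, lymphocytes, monocytes, and neutrophils". It then states: "Total and differential WBC counts will not be provided to the Investigator to maintain the treatment blind during the Induction and Maintenance Period". It adds: "These parameters and alerts for these parameters will be monitored by the PPD Safety Surveillance team".

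Section 12.6 describes the blind again, in different terms: "During the treatment period, all Total WBC and WBC differential results will be blinded". It continues: "If any of the following results are observed, the Investigator will be notified and asked to repeat the laboratory tests within approximately 7 days". The list that follows has three entries: "Absolute lymphocyte count [ALC] < 200 cells"/µL, ANC below 1000 cells/µL, and total WBC above 20,000 cells/µL. SAP section 6.20.6 repeats the withholding of total and differential counts and gives no period limit.

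**The concern.** A mandatory stop rule is only as good as the information that reaches whoever applies it. Here one input is a laboratory value that the same protocol keeps from the investigator, and the investigator is asked, directly after the criteria, to establish causality.

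For other blinded counts that it wanted acted on, the protocol wrote the relay into 12.6: a threshold, a notice to the site and a repeat test. Eosinophils have no such relay, although they feed a permanent stop.

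Two things are at stake. A patient with raised transaminases and no symptoms could meet the criterion without the site knowing. And a site that wants to apply the rule may order a local differential, which also shows lymphocytes. Section 11.3 warns that local testing may unblind.

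**Working it through.** The plan gives no figure to reproduce. The check is a cross-reading, with one line of arithmetic.

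1. **What the rule needs.** Protocol 12.6, fourth condition: an ALT or AST value, plus at least one of seven findings joined by and/or. Six are clinical. The seventh, eosinophilia above 5%, is a laboratory value.
2. **Where that value sits.** Protocol 11.3 lists eosinophils in the WBC differential.
3. **Who does not see it.** The investigator: during the Induction and Maintenance Periods under 11.3, during the treatment period under 12.6, and with no period stated in SAP 6.20.6.
4. **Who does see it.** The CRO's safety surveillance team (11.3). No sentence tells that team to compare eosinophils with ALT or AST, or to inform the site.
5. **What is relayed.** ALC <200, ANC <1000 and total WBC >20,000 cells/µL (12.6). There is no eosinophil entry and no combined transaminase and eosinophil entry.
6. **Could the three listed alerts stand in for an eosinophil alert?** Take assumed counts of WBC 6,000, ALC 1,000 and ANC 4,000 cells/µL, with 5.1% eosinophils.
   - Eosinophils: 0.051 × 6,000 = 306 cells/µL. As 5.1% > 5%, the eosinophilia finding is met.
   - ALC 1,000 is not below 200; ANC 4,000 is not below 1000; WBC 6,000 is not above 20,000. No alert fires.
   - So the listed alerts do not cover the criterion. The counts only illustrate this.
7. **How far the gap reaches.** Within the fourth condition, 7 − 1 = 6 findings can be seen or elicited at the site. Of the four conditions, 4 − 1 = 3 do not use the differential: above 8x ULN, confirmed above 5x ULN, and above 3x ULN with raised bilirubin or INR. Only a patient above 3x ULN, with no other evident cause and with eosinophilia as the sole accompanying finding, depends on the missing relay.
8. **Is the result available when needed?** Table 1 schedules hematology and chemistry at the same visits. The transaminase retests in 11.5 and 12.6, within 14 days and then weekly if confirmed, do not say whether a differential is drawn.
9. **Which period.** The wordings of 11.3 and 12.6 differ. Under the first, the blind on the differential ends with the Maintenance Period. The second could be read to extend into the Open-Label Period.

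**The case against.** The strongest reply is that the rule can still operate. The central team sees the differential and monitors alerts for it. The stop sentence is passive and names no decision-maker, and section 9.7.2 lets a safety withdrawal be assessed by the treating investigator, the Medical Monitor or both. Section 11.3 leaves extra safety tests to the investigator's judgement and discourages local laboratories without forbidding them. It also refers to a study laboratory manual covering how abnormal values are alerted, and section 12.3 mentions a safety management plan. Either could already contain an eosinophil alert. Finally, 11.5 separately requires a stop at confirmed transaminases above 5x ULN, and 9.7.1 lets the investigator stop drug when continuing is not in the patient's interest.

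Most of this stands, and it limits the point. A reader might infer that the criterion can never be triggered, or that the hepatic stop rule as a whole fails; the documents support neither. A reader might also count all of the approximately 180 randomized patients as affected. They are all subject to the rule, but the gap bites only in the subset defined above.

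A further tempting inference is that a percentage criterion is easier to meet on active drug, because a fall in lymphocytes shrinks the denominator. Section 12.6 says only that ALC falls. The inference also needs the other cell counts to stay constant and starting values close to 5%, which the documents do not give, and it shows no disagreement between passages. I do not rely on it.

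What the reply does not remove is the omission itself. Seeing a result is not the same as being told to pass it on, and the protocol puts its other blinded-count alerts in its own text.

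**Conclusion.** The point holds in a limited form. Sections 11.3 and 12.6 make a result unavailable to the site, 12.6 also makes that result sufficient, alongside ALT or AST above 3x ULN, for a permanent stop, and neither document states how the two are joined. Following the text as written could leave a patient on drug when the protocol says to stop.

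Few patients would be expected to fall in the affected group. The available text gives no rate of isolated eosinophilia at that transaminase level, so I put no number on it. It is nonetheless the group for which a laboratory finding matters most: raised transaminases without symptoms, in a trial that names hepatotoxicity as an event of interest.

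The conclusion rests on the protocol and SAP alone. If the laboratory manual or safety management plan already holds the alert, what remains is to state it in 12.6 and make the sections consistent.

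**What to change.** Reconcile sections 11.3 and 12.6 as follows:

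- State in 12.6 that, whenever ALT or AST exceeds 3x ULN in a patient whose differential is blinded, the central safety team that already monitors the differential checks the eosinophil result against the stated criterion. It then tells the investigator and the Medical Monitor yes or no, without releasing the differential. Carry the same step into the laboratory manual and safety management plan if it is not already there.
- State whether the ALT/AST retests include a differential.
- Use one description of the blinded period in 11.3 and 12.6, and match SAP 6.20.6 to it.

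The threshold and the stop rule itself remain for the sponsor to decide.

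The cost is about one paragraph of protocol text and one alert in the central laboratory specification. Scheduled visits need no new test, because hematology and chemistry are already drawn together; a differential may have to be added at retests. A yes message discloses one hematology fact for a few patients, which is less than a local differential would reveal.
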